5.1 Specific Aims

Despite the use of evidence-based psychotherapies (EBPs) for posttraumatic stress disorder (PTSD), two-thirds of Veterans report continued problems as indicated by sustained PTSD symptoms, functional impairment, and poor social functioning after PTSD treatment.¹ Increasing evidence suggests that for some Veterans, non-response to PTSD treatments may be in part because EBPs do not address co-occurring moral injury (MI) distress^{2,3} and shared features (e.g., emotional numbing). Existing PTSD treatments are also limited as they do not directly facilitate building positive resources to enhance social functioning. Given the prevalence of trauma distress^{4,5} and the limitations of existing treatments, novel approaches are needed to (1) target both PTSD and MI and (2) directly impact psychosocial growth and functional recovery. To address this need, this study will pilot a new positive psychology intervention, as current positive psychology interventions effectively enhance well-being through cultivating positive emotions. This pilot trial focuses on moral elevation-a distinct, positive emotional state described as feeling uplifted and inspired by others' virtuous actions⁶—which is relevant to PTSD and MI recovery because it encourages social engagement and serves as a template for interpreting the world in a healthier way. Higher levels of moral elevation are associated with fewer mental health symptoms,⁷ a strong desire to engage with others, and increased prosocial behavior.⁸⁻¹⁰ Promising preliminary results have showed that moral elevation is negatively correlated with PTSD avoidance symptoms and MI.¹¹ Although there is evidence that moral elevation may benefit those with significant trauma distress, it is unknown whether moral elevation can be cultivated in Veterans with PTSD and MI and if such an intervention would be accepted by this population. The lack of such knowledge is an important problem because the capacity of moral elevation to target psychological health and social functioning could be used to facilitate trauma recovery for Veterans.

Our long-term goal is to improve trauma treatment so that it effectively targets both PTSD and MI distress, while simultaneously facilitating psychosocial growth and functional recovery in Veterans. The **objective of the present study** is to assess whether a brief, web-based moral elevation intervention is a feasible and acceptable therapeutic approach for Veterans of Operations Enduring Freedom (OEF), Iraqi Freedom (OIF), and New Dawn (OND). If Veterans are willing and able to complete a web-based moral elevation intervention and it has beneficial effects, then it could be utilized as a potential catalyst for cognitive, emotional, and behavioral experiences linked to trauma recovery. Further, this study will provide pilot data for a future comprehensive test of a moral elevation intervention in a clinical trial that could determine if this novel approach leads to beneficial outcomes.

We plan to accomplish this objective through the following two specific aims:

Aim 1: Conduct a pilot trial of an 8-session, 1-month-long web-based moral elevation intervention to assess:

- a. Feasibility of recruitment, retention, and completion of the intervention;
- b. Ability of the intervention to elicit moral elevation in OEF/OIF/OND Veterans who have experienced amorally injurious event and meet criteria for a current diagnosis of PTSD; and

c. Acceptability of and satisfaction with moral elevation exercises, the intervention's general structure, and proposed methodology through qualitative measurement and analysis.

Aim 2: Conduct a no-treatment condition (i.e., comparison group) in preparation for future randomized controlled trials (RCTs) to assess:

- a. Feasibility of randomization and completion of a no-treatment condition; and
- b. Retention and completion of assessments at baseline, repeated measures, and follow-up.

The proposed work is innovative because it aims to elicit the benefits of moral elevation to target trauma distress—a novel approach that is not currently used to treat Veterans, but is a promising area of research with significant support in other populations. We expect that OEF/OIF/OND Veterans will be able to complete this online intervention, and that their feedback will inform how to best implement moral elevation interventions in a Veteran population. Qualitative data will also be used to develop study methods for a future RCT to test the efficacy of a moral elevation intervention for targeting desired outcomes. Positive results from this study would indicate that this low-cost, web-based intervention could be easily disseminated to a wide range of Veterans and clinics, spanning from Veterans who are not actively engaged in care to those attending in-person treatment. Further, with replication, these findings could implicate moral elevation as a transdiagnostic tool that positively impacts complex psychological health needs (i.e., PTSD and MI), while also facilitating recovery through enhanced social functioning.

Keywords: web-based intervention, pilot study, moral elevation, veterans, PTSD, moral injury

5.2 Rationale for Research

A. Treating PTSD and MI: Overview and Gaps. Combat Veterans are at increased risk for posttraumatic stress disorder (PTSD) and moral injury (MI). PTSD is characterized by exposure to a traumatic event and 4 core symptom clusters: re-experiencing or intrusion, avoidance, changes in cognitions and mood, and arousal symptoms.¹² MI occurs when a person witnesses or performs an act that violates their deeply held values and is associated with clinically significant levels of guilt, shame, and anger.¹³⁻¹⁴ MI is an emerging concern for Operations Enduring Freedom (OEF), Iraqi Freedom (OIF), and New Dawn (OND) Veterans, with upwards of 80% of Veterans reporting to have experienced a potentially morally injurious event (e.g., I saw things that were morally wrong),¹⁵ and 38% endorsing significant distress directly related to at least 1 morally injurious event.¹⁶ Treatment for PTSD and MI is a high priority because both are associated with poor mental health outcomes, functional impairment, decreased social engagement,¹⁷⁻¹⁹ and thus, poor reintegration into civilian life. Although distinct, PTSD and MI can co-occur^{20,21} and share features (e.g., emotional numbing, isolation) that could be more effectively targeted than by current therapeutic approaches; therefore, treatments that adequately address both PTSD and MI are needed. Trauma treatments available to Veterans primarily consist of psychotherapy for PTSD; however, current approaches are limited for two main reasons: 1) Results from clinical trials indicate that two-thirds of Veterans who complete evidence-based PTSD psychotherapies report continued or clinically elevated symptoms at follow-up.¹ Research also suggests that PTSD treatments are not effective for MI distress, a shame- or guilt-based response distinct from the fear-based response in PTSD.^{2,3} Accordingly, clinicians report concerns that PTSD therapies do not effectively treat MI distress.²² 2) Despite a call to facilitate psychosocial growth and maximize recovery in trauma-exposed Veterans,^{21,22} psychotherapy typically aims to alleviate symptoms and does not directly target building positive resources that increase social functioning. Therefore, there is a major need for novel treatment approaches that (1) target both PTSD and MI distress following combat trauma, and (2) directly impact psychosocial growth and functional recovery.

B. Moral Elevation: Definition. A potential way to address the areas wherein trauma treatment falls short is through relevant positive psychology constructs, such as moral elevation (hereafter, "elevation"), a positive emotional state that encourages social engagement. Elevation is specifically defined by a distinct trigger and action tendency. Elevation is triggered after witnessing another person perform a virtuous act (e.g., courage, generosity), which can lead the observer to feel inspired and uplifted, accompanied by positive physical sensations (e.g., tears, lump in the throat). This is typically followed by a strong desire to emulate the witnessed virtuous behavior (e.g., I want to act generously too), become a better person, and engage with others. These distinct benefits of elevation are related to improved psychological health, as evidenced in a study that linked daily elevation to lower daily symptoms of anxiety, dysphoria, and hostility in a civilian sample of anxious and depressed patients.⁷ In experimental and observational studies with nonclinical populations, elevation is linked to features of social engagement such as increased affiliation urges, greater responsiveness to others' needs, increased compassion, and more prosocial behavior.⁸⁻¹⁰ Thus, elevation is a causal emotion for improving psychological health and social functioning.

C. Theoretical Framework. While trauma leads to the strong negative effects of PTSD and MI, research indicates elevation is antithetical to trauma distress and leads to positive effects on

psychological health and social functioning. Thus, elevation may have the capacity to reverse the negative effects of PTSD and MI through emotional, cognitive, and behavioral experiences linked to trauma recovery. As many Veterans with PTSD or MI report difficulty experiencing positive feelings,^{21,23} repeated exposure to positive emotions like elevation may target the numbing features of trauma distress. Interventions that elicit elevation and increase a Veterans' tendency to be aware of others' virtuous behavior (i.e., recognizing the goodness in others) may aid in reducing maladaptive beliefs (e.g., You cannot trust other people¹³). The action tendency may also motivate Veterans to engage in behaviors that require greater social interaction, counteracting isolation tendencies and increasing the likelihood of connecting with others or reintegrating into civilian life.

D. Significance. There is a critical need for new treatments that improve the effectiveness of trauma treatment for both PTSD and MI, while also directly impacting psychosocial growth and functional recovery in Veterans. This study aims to address this need by piloting a web-based elevation intervention designed to elicit elevation and its benefits. Using elevation as a therapeutic tool falls within the broader theory of positive psychology—an emerging field with effective interventions aimed to enhance well-being through positive emotions.²⁴ such as elevation. Studies have yet to test an elevation-based intervention in a trauma-exposed population. This project could advance the scientific knowledge of trauma recovery and positive psychology by identifying elevation as an innovative tool for clinical practice, which would extend trauma treatment beyond the amelioration of distressing symptoms to also encourage enhanced social functioning and psychosocial growth among trauma-exposed Veterans. This project also has the potential to affect the delivery of trauma recovery services by testing a webbased elevation intervention that increases the accessibility of growth-oriented therapeutic approaches, impacting Veterans already engaged in care who wish to further enhance their wellbeing as well as Veterans who may be reluctant to initiate in-person treatment due to stigma or impairing avoidance symptoms associated with trauma distress.

6. Design and Methods

6.1 Methods Objectives

A 2-year pilot trial of a web-based elevation intervention for Veterans who experienced significant distress regarding a morally injurious event and with a current diagnosis of PTSD is proposed to assess: 1) feasibility of recruitment, retention, and completion of 8 sessions over a 1-month period; 2) ability of the intervention to elicit elevation; 3) acceptability of and satisfaction with elevation exercises, the intervention's general structure, and proposed methods; and 4) feasibility of randomization to a no-treatment condition to be used in future randomized controlled trials (RCTs) and completion of all assessments within this condition.

Participants will complete self-report measures that assess PTSD symptoms, MI distress, and social functioning as measured by prosocial behavior and quality of social relationships at baseline (BL; i.e., pre-intervention) and follow-up (FU; i.e., post-intervention). To supplement self-report measures and fully capture the potential impact on social functioning, each participant will invite 1 significant other (SO; e.g., spouse, friend) to complete measures based on observations of the Veteran's social behavior at baseline and follow-up. Veteran participants will be randomly assigned to an elevation intervention condition or a no-treatment control condition. Each condition comprises 2 web-based sessions per week (Monday and Thursday) for 1 month, totaling 8 sessions (<30 min/session).

Veteran participants will also complete repeated measures at each session, and Veterans in the intervention condition will complete an individual qualitative interview (~1 hr) with a qualified member of the study team at follow-up. The duration of the entire study for each Veteran participant is 6 weeks total. See Table 1 for a study timeline.

	Year	Pre		1			2	
	Quarte	Pre	12	2 3	8 4	1	2	34
Pre-Award Activities								
Obtain IRB approval; Hire psychology technician; Prepare online materials								
Training & Preparation								
Train psychology technician; Prepare recruitment/screening materials; Obtai eligible participants via VA CDW	n list of							
Conduct Pilot Study								
Telephone/eligibility screening assessment (n=5/month; total n=60)								
BL assessment & randomization (n=4/month; total n=48)								
8 online sessions (n=2/month; total n=24)								
FU assessment & qualitative interview* (n=2/month; total n=24) *Qualitative interview to be completed by treatment condition only								
Analyses								
Analyses of qualitative data; Analyses of recruitment & retention data								
Formulate future research (RCT grant proposal) based on results								
Disseminate results via national academic conferences & scientific journals								

Table 1. Study Timeline, Procedures, and Recruitment Goals

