6.2 Participants

The targeted sample size for study completion is 24 Veterans, 12 per group.²⁵ Given that positive psychology web-based interventions have an average attrition rate of approximately 50% for clinical populations,²⁶ we aim to recruit and randomize 48 eligible Veterans within the initial baseline assessment to account for the expected attrition and to reach the goal of 24 Veteran completers. Specifically, "eligible" status is determined by passing the initial pre-screen over the phone, then passing the final screen for all inclusion and exclusion criteria after completion of the baseline assessment. For all Veterans who are determined eligible after the baseline appointment, one Significant Other will be recruited to complete observational measures for each Veteran. Therefore, we aim to recruit 48 eligible Veterans and 48 corresponding Significant Others. Given that participants need to verbally consent to the baseline appointment to determine final eligibility for full enrollment and randomization, it is possible that some consenting Veterans will not meet the inclusion criteria after consenting at baseline. In other words, consent does not automatically equal randomization. Any Veteran who consented but was then deemed ineligible based on the results of the baseline assessment would not be considered as contributing to the minimum sample size of 48 eligible Veterans. We anticipate that 2 out of every 3 participants is likely to be eligible after conducting a baseline appointment; therefore, we aim to obtain verbal consent from approximately 72 Veterans to meet the sample size required for eligible and enrolled Veterans. When combining the 48 Significant Others who are expected to consent after a Veteran is enrolled and randomized, we aim to recruit a total of 120 participants.

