6.6 Screening Procedures

The brief screening assessment by telephone will be conducted by a trained psychology technician. The screening assessment (see Appendix C) includes questions regarding inclusion criteria and the administration of self-report questionnaires (MIES & PCL-5). A brief screening assessment should help minimize participant burden, as those who are not eligible will be saved time associated with completing a full baseline assessment. If the Veteran is determined to be ineligible based on the eligibility screening procedure, we will not collect any personally identifying information. For veterans determined to be eligible, we will collect identifying information for the purpose of scheduling a baseline appointment to determine final eligibility. This identifying information will be recorded on an electronic screen registry of initially-eligible participants, including Screen ID#, date of screen, salutation, name, contact information, whether or not it is ok to leave telephone messages (e.g., for appointment reminders), the appointment date/time, enrollment date, and reason not enrolled (e.g., unable to schedule, no longer has time to participate). This information is stored in a password-protected registry on the secure S:\drive (S:\Research\2. PROJECTS\[name]\MOVED). Following the pre-screen (phone screen), for those deemed initially eligible, a cover letter will be mailed to the Veteran in advance of the baseline assessment appointment along with a document that reviews all aspects of participating in the study (i.e., Review of Research Participation), direct deposit form. Coded hardcopy eligibility screening documents will be stored in separate files for those deemed initially eligible versus ineligible. Pre-screen information will be used in aggregate to report the recruitment process (e.g., number screened, number eligible, number ineligible, percentage/reasons for ineligibility, etc). In the event that a Veteran displays a high level of suicidality or reports that they are in crisis during the telephone screen, research staff will assess the risk and consult with an on-site, licensed clinical psychologist or psychiatrist to determine an appropriate course of action. The principal investigator will be notified of any such incidents immediately. The principal investigator will supervise all assessments. Notably, all research staff are trained in suicide prevention and risk assessment.

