6.7 Informed Consent Procedures

Veteran Participants: Following the pre-screen, study staff will schedule a baseline assessment appointment to be completed by phone. A copy of the Review of Research Participation Form will be mailed to the Veteran in advance of the baseline appointment for the Veteran to read and consider participation. This procedure will reduce participants' time burden on the day of the assessment, as Veterans will have had the time to read and consider the Review of Research Participation Form prior to the initial baseline appointment. At the start of the appointment, Veterans will be asked if s/he had a chance to read the Review of Research Participation Form, and if not, will be asked to read the form carefully at that time. It should be noted that, regardless of whether or not participants read the Review of Research Participation Form ahead of time, the study staff member will always explain the nature of the study to participants at the beginning of the appointment, as well as the potential risks/benefits of participating in the study. For this study, we will obtain verbal consent, rather than written consent. Verbal consent will only be obtained prior to the baseline assessment and will not be obtained until the researcher is satisfied that the participant has a good understanding of the risks/benefits of participating in the study. All team members with patient contact including consenting procedure will be appropriately trained, assigned duties and documented as per VA regulations

Significant Other Participants: Upon obtaining informed consent from the Veteran participant to allow the study team to initiate contact with the Significant Other (SO), study personnel will call the SO and obtain verbal consent over the phone. This procedure requires a waiver of consent and waiver of HIPAA authorization on behalf of the Significant Other Participant (attached).

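### Table 1's goal of 60 telephone screens is at least 12 too few for the roughly 72 baseline consents that Section 6.2 needs in order to randomise 48 Veterans

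*Protocol*

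**What the plan says.** Table 1 in protocol Section 6.1 is captioned "Table 1. Study Timeline, Procedures, and Recruitment Goals". Its screening row reads "Telephone/eligibility screening assessment (n=5/month; total n=60", and the next row reads "BL assessment & randomization (n=4/month; total n=48". The later rows, for the online sessions and for follow-up, each give 2 per month and a total of 24.

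Section 6.2 builds the sample in the other direction. It starts from 24 completers, allows for about 50% attrition and so aims to randomise 48. It then says "We anticipate that 2 out of every 3 participants is likely to be eligible after conducting a baseline appointment", and concludes that "we aim to obtain verbal consent from approximately 72 Veterans to meet the sample size required for eligible and enrolled Veterans". With 48 Significant Others added, the overall recruitment target is 120.

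The order of the steps is stated several times. Section 6.2 says that eligibility "status is determined by passing the initial pre-screen over the phone, then passing the final screen for all inclusion and exclusion criteria". Section 6.6 says "For veterans determined to be eligible, we will collect identifying information for the purpose of scheduling a baseline appointment to determine final eligibility". Section 6.7 says "Following the pre-screen, study staff will schedule a baseline assessment appointment to be completed by phone". Section 8.1 B likewise has each potential Veteran participant screened by telephone before a baseline assessment is scheduled.

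**The concern.** Veterans who consent at baseline are a subset of those who were screened, so the number screened cannot be smaller than the number consenting. Table 1 has it smaller: 60 screens against about 72 baseline consents in Section 6.2.

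What is at stake is the recruitment plan, not an inferential result. Feasibility of recruitment is Aim 1.A, and Section 6.11 will examine numbers and rates from screening and enrolment through to retention. The pilot is also meant to prepare a later randomised trial. With one screening yield implied by Table 1 and a lower one by Section 6.2, there is no single planned figure against which to set the observed recruitment or from which to plan the next trial's screening load.

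**Working it through.** **Inputs, all from the protocol**
- Table 1: 60 screens at 5 per month; 48 baseline assessments with randomisation at 4 per month; 24 completing at 2 per month.
- Section 6.2: 24 completers, about 50% attrition, 48 randomised, 2/3 eligible after baseline, about 72 baseline consents, 120 participants in all.
- Not given anywhere: the share of screened Veterans who pass the screen and go on to consent at baseline.

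**Reproducing Section 6.2**
- Randomised = completers ÷ (1 − attrition) = 24 ÷ 0.5 = 48.
- Baseline consents = randomised ÷ share eligible = 48 ÷ (2/3) = 72.
- Total participants = 72 Veterans + 48 Significant Others = 120.

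All three match the text, so Section 6.2 is internally consistent.

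**Table 1 on its own terms**
- Implied duration = 60/5 = 48/4 = 24/2 = 12 months. This is back-calculated, because the quarter markings are not legible in the text available for review. The rows agree with their own monthly rates.
- Implied yield from screening to randomisation = 48/60 = 80%.

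**Putting the two together**
- Yield at the baseline step alone in Section 6.2 = 48/72 = 66.7%. The yield from screening to randomisation cannot be higher than this, and Table 1 implies 80%.
- Minimum screens = 72 ÷ r, where r is the proportion of screened Veterans who pass and then consent at baseline. At the most favourable value, r = 1, this is 72.
- Shortfall = 72 − 60 = 12 screens; 12/72 = 16.7% below the need; 72/60 = 1.20, so 20% more screening than stated.
- Rate over the implied 12 months = 72/12 = 6 per month, against 5. At 5 per month, 72 screens would take 72/5 = 14.4 months.
- If screening did stop at 60 and everyone passed and consented, the expected number randomised would be 60 × 2/3 = 40, which is 8 short of 48.

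**Range over the unstated rate r (assumed values, for illustration only)**

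| r | Screens needed (72 ÷ r, rounded up) | Above 60 by |
|---|---|---|
| 100% | 72 | 12 |
| 90% | 80 | 20 |
| 80% | 90 | 30 |
| 70% | 103 | 43 |
| 60% | 120 | 60 |
| 50% | 144 | 84 |

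**Other readings**
- If 60 means Veterans who passed the screen, it is still below 72.
- Section 8.2 A.1 also mentions verbal consent before the telephone screen. If the 72 were counted there, all 72 would go on to be screened, so the gap remains.
- The in-person option in Section 6.5 is the same screening interview, held before baseline.

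**The case against.** The strongest case on the other side concerns weight. Section 6.1 introduces Table 1 as a timeline, while Section 6.2 governs the sample size and sets out its funnel correctly, so a team that follows Section 6.2 will recruit the right number. Nothing stops screening at 60. Section 6.5 allows repeat database queries at an adjustable frequency with up to 100,000 names, and Section 8.2 A.1 adds in-person recruitment if goals are not met. Neither Section 6.11 nor the SAP uses 60 as a threshold, denominator or trigger. All of this stands and limits the consequence. It also means that the figure of 40 randomised describes a case the protocol does not plan for.

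A second objection is about precision. Section 6.2 says approximately 72 and gives an expected eligibility share, not a ceiling. That is fair: both the floor of 72 and the gap of 12 are planning values. It does not close the gap, because 60 consents at the expected share give 40 randomised, not 48.

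A third is that the combined baseline-and-randomisation row is not wrong, since 48 is the number expected to complete both steps. That also stands. The row merely omits the 72 − 48 = 24 or so Veterans expected to be assessed at baseline and found ineligible.

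**Conclusion.** The point holds, as a minor one. Table 1's screening goal contradicts the funnel in Section 6.2 by at least 12 screens (60 against a minimum of 72). This rests on Section 6.2's own two-in-three eligibility share and on the stated order of screening before baseline. Twelve is the smallest gap, reached only if every screened Veteran passes and consents. The screen applies PCL-5, MIES, internet-access and willingness criteria, so the real gap is likely to be larger, but the documents give no rate from which to size it. The monthly comparison also assumes the back-calculated 12 months; the totals do not. The error is in a stated planning figure. It does not limit the sample of 48 and affects no analysis.

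**What to change.** Reconcile Table 1 with Section 6.2 in two places.

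1. Restate the screening goal as 72 ÷ r, with r stated by the sponsor and defined to cover both passing the screen and consenting at baseline. An assumed 80%, for example, would give 90. If no rate can be given, state at least 72 (6 per month over the implied 12 months) and say that this is a floor that allows for no losses.
2. Split the baseline row so that about 72 baseline consents appear separately from 48 randomised.

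The cost is a table correction and a somewhat higher stated screening load, at least 6 per month instead of 5. The target of 48 randomised and all planned analyses are unchanged.
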